11.0 Statistical Considerations

Sample Size Justification and Power Analysis

This pilot RCT is not designed to detect statistically significant differences. We chose N=64, as it is sufficient to yield the expected outcomes and is feasible within the R21 constraints. Assuming an attrition rate of $\leq 20\%$,¹¹⁷ we will have ≥ 50 completers (25/arm). With 50 completers and type I error rate=5%, we will have 55%, 68%, 79%, and 88% power to detect a $d=0.60, 0.70, 0.80$, and 0.90, respectively. We observed a $d=0.90$ for CBT for depression on fasting glucose in depressed primary care patients (see C2).

Primary Aim Analytic Plan

Analyses will use the intent-to-treat approach.¹¹⁸ Tests will be two-tailed with $p<.05$ considered statistically significant. Supplemental analyses of completers and analyses employing multiple imputation (SAS mi and mianalyze) will be performed. We will assess for group differences in baseline factors. Due to randomization, we do not expect differences. Even so, baseline differences will be taken into account when interpreting results, and baseline factors that differ between groups will be added as covariates in sensitivity analyses. We will also add expectancy and attention as covariates in sensitivity analyses.

We will evaluate H1 and H2 (eIMPACT-DM patients will exhibit greater improvement in A1c and HOMA score) using linear mixed modeling (SAS proc mixed) with an unstructured covariance matrix. Subject will be a random effect, and treatment group, time, and their interaction will be fixed effects. Separate models will be run for the primary (A1c) and secondary (HOMA score) outcomes. Treatment group x time interactions would indicate statistically significant treatment effects. For both A1c and HOMA score, we will report the group means and standard errors; regression coefficients, 95% CIs, and p-values; and effect sizes (d 's). We will consider an absolute group difference in post-treatment A1c of $\geq 0.3\%$ ($d=0.50$) to be clinically important (e.g., 5.9% for eIMPACT-DM group versus 6.2% for AC group; $d=0.50$). This A1c difference corresponds to annualized diabetes incidence rate of 4.0% for the eIMPACT-DM group versus 7.0% for the AC group.⁷⁰ Because there is no absolute cut point distinguishing between normal and abnormal HOMA scores,¹¹⁹ we will consider a $d\geq 0.50$ (moderate effect size⁶⁵) as clinically important. If we find that the eIMPACT-DM produces clinically important improvements in A1c and HOMA score (d 's ≥ 0.50), it would pave the way to an R01-level RCT by (1) generating critical proof-of-concept data to support the premise and (2) providing preliminary effect sizes for eIMPACT-DM on A1c and HOMA score. Of note, the effect size estimate used in the primary power analysis for the future RCT will be based on the minimal clinically important difference in A1c instead of solely on this RCT's results, as pilot studies tend to overestimate or underestimate true effect sizes.¹²⁰ We will use this RCT's results, along with other relevant data, to make a strong case that the selected effect size estimate is plausible and achievable.

A set of planned subgroup analyses will be performed including only participants with pre-treatment A1c values between 5.70%-6.49%. Another set of planned subgroup analyses will explore whether history of COVID-19 infection (defined as history of a positive COVID-19 test at trial entry) moderates the effect of eIMPACT-DM on A1c and HOMA score.

Exploratory Aim Analytic Plan

To explore whether somatic depressive symptoms moderate the effect of eIMPACT-DM on A1c and HOMA score, we will rerun the Primary Aim models stratified by somatic symptoms group. We expect ~60% of patients to have hyperphagia and/or hypersomnia and thus be coded as "yes" on the somatic symptoms group variable (see C3). The remaining patients will be coded as "no." We anticipate larger effect sizes for the somatic symptoms group. We will consider an effect size difference between groups of $d\geq 0.50$ to be clinically meaningful (e.g.,

$d=0.75$ vs. 0.25). We will compute effect sizes of treatment group x somatic symptoms group x time interactions for A1c and HOMA score; however, we expect these to be nonsignificant due to lower power. If we find clinically important effect size differences between those with vs. without somatic depressive symptoms, we will modify the design of the R01-level RCT as follows – recruitment: enroll 50% with and 50% without these symptoms; randomization: stratify on presence of these symptoms; and sample size: ensure sufficient power to detect 3-way interactions.

A set of planned subgroup analyses will be performed including only participants with pre-treatment A1c values between 5.70%-6.49%. Another set of planned subgroup analyses will explore whether history of COVID-19 infection (defined as history of a positive COVID-19 test at trial entry) moderates the effect of eIMPACT-DM on A1c and HOMA score.

Incident Diabetes

We will also explore whether eIMPACT-DM patients show a clinically relevant reduction ($\geq 25\%$ lower relative risk) in incident diabetes by performing a Cox model with treatment group predicting time to diabetes onset.

Sex as a Relevant Biological Variable

In exploratory analyses, we will examine sex as a moderator of treatment effects on all outcomes by testing treatment group x sex x time interactions in the Primary Aim models. In addition, we will examine whether there is sex difference in the likelihood of being classified as having a somatic presentation of depression (i.e., those with hyperphagia and/or hypersomnia) at baseline. If a sex difference is found, it would influence the design of the future definitive RCT – e.g., we would likely additionally stratify randomization by sex.

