Using the 4.8% randomization rate from our eIMPACT Trial, we estimate that we will need to screen ≈26/week to randomize 64 patients over the 1-year recruitment period. In the eIMPACT Trial, which has similar but more restrictive eligibility criteria, 4.8% (216/4539) of approached patients were randomized. Most ineligible patients did not meet the current depressive disorder inclusion criterion. We conducted an EMR search and identified 47,361 demographically and medically eligible Eskenazi primary care patients with no history of diabetes (63% women, 48% non-Hispanic Black, 20% Hispanic/Latinx), of whom 9,876 (21%) fell on the high priority list (positive for a prediabetes marker). ResNet leadership agrees that our approach and our randomization rate and target are feasible. We will be able to start recruitment immediately because personnel and protocols are in place from the eIMPACT Trial.

Randomization

1:1 randomization⁸⁸ will be stratified by A1c ($\leq 6.09\%$, 6.10-6.49%) and somatic depressive symptoms (yes, no) at pre-treatment using random number sequences.⁸⁸ Sequentially numbered, opaque, sealed envelopes containing group assignment will be prepared by the study statistician ([name]).

Blinding

All outcomes assessors will be blinded to group assignment to ensure unbiased results. The investigators and interventionists will have no data collection responsibilities, and the patients will be explicitly instructed not to reveal their group assignment to the outcomes assessors.

[figure not shown]
Retention Plan

We will use the successful practices of our eIMPACT Trial to retain participants over the 6-month study period. First, we will implement Mason's procedures for minimizing attrition – e.g., collecting extensive contact information for patients and at least two secondary contacts, stressing the study timeline and scientific importance of study completion at enrollment, and

[figure not shown]

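### Sensitivity-analysis covariates are selected by observed baseline imbalance, which under randomisation is chance; a short set fixed in advance should replace the rule.

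*Combined protocol and SAP*

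**What the plan says.** Section 11.0, Primary Aim Analytic Plan, says that the arms will be compared on baseline factors. It adds "Due to randomization, we do not expect differences", and then gives differences two uses: "baseline differences will be taken into account when interpreting results", and "baseline factors that differ between groups will be added as covariates in sensitivity analyses". No list of candidate factors is given, and no definition of differing. The only threshold in the section is general: "Tests will be two-tailed with $p<.05$ considered statistically significant". Nothing says whether a covariate enters as a main effect or also interacts with time.

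Other sensitivity covariates are named in advance: "We will also add expectancy and attention as covariates in sensitivity analyses".

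The primary model for A1c and HOMA is a linear mixed model on the pre- and post-treatment values, with group, time and group x time as fixed effects. The treatment effect is the group x time term. No covariate is listed.

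Section 5.0, Randomization, stratifies 1:1 allocation by A1c (two bands) "and somatic depressive symptoms (yes, no) at pre-treatment using random number sequences". Neither factor is listed in the primary model or named for a sensitivity model.

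**The concern.** If randomisation was carried out properly, a baseline difference between arms is chance. Selecting on it says nothing about whether the factor predicts A1c or HOMA. An unrelated questionnaire score can enter, a strong predictor that happens to be balanced stays out, and the factors that stratification is meant to balance will seldom be chosen. Without a list or criterion, the adjusted model can be settled only after the arms have been compared, and the analyst has latitude over what counts as a difference.

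At stake is how useful the check is. A sensitivity analysis should answer a question fixed beforehand. This one varies with the accidents of a single allocation, and the accompanying clause lets the same accidents colour the reading of the primary result.

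**Working it through.** **1. The plan's own figure.** Inputs from section 11.0: "We chose N=64, as it is sufficient to yield the expected outcomes and is feasible within the R21 constraints", attrition up to 20%, and "we will have ≥ 50 completers (25/arm"). 64 x 0.8 = 51.2, consistent with at least 50. Two-sample t-test power (noncentral t, 48 df, two-sided 5%) at d = 0.60, 0.70, 0.80, 0.90 is 54.7%, 67.9%, 79.2%, 87.7%, against the stated 55%, 68%, 79%, 88%. The figures reproduce, and n = 50 is used below.

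**2. How often the rule selects something by chance.** Assume that differing means p<0.05 and that k candidates are independent. Then P(at least one) = 1 - 0.95^k.

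| k | P(at least one) |
|---|---|
| 10 | 40% |
| 20 | 64% |
| 30 | 79% |

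The range of k is an assumption; the measures listed in section 3.0 suggest roughly 20-30.

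**3. One flagged covariate.** A factor just at p = 0.05 has arm-covariate r² = t²/(t² + 48) = 2.0106²/(2.0106² + 48) = 0.078. With within-arm outcome correlation rho,

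SE ratio (adjusted/unadjusted) = sqrt[(1 - rho²)/(1 - r²) x (n - 2)/(n - 3)].

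At rho = 0: sqrt[(1/0.922) x (48/47)] = 1.05.

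| rho | 0 | 0.2 | 0.3 | 0.4 | 0.5 | 0.6 |
|---|---|---|---|---|---|---|
| SE ratio | 1.05 | 1.03 | 1.00 | 0.96 | 0.91 | 0.84 |

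Break-even is at rho of about 0.3. The documents give no rho.

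**4. The whole rule.** Simulation: n = 50, select at p<0.05, then regress change on arm and the selected factors; 20,000 runs per row. Entries are the SD of the estimated effect, in outcome SD units.

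| Candidates | Unadjusted | Rule | Change |
|---|---|---|---|
| 10, none prognostic | 0.283 | 0.292 | +3% |
| 20, none prognostic | 0.284 | 0.302 | +6% |
| 30, none prognostic | 0.282 | 0.308 | +10% |
| 20, two prognostic, R² 0.10 | 0.283 | 0.297 | +5% |
| 20, two prognostic, R² 0.30 | 0.283 | 0.289 | +2% |
| 20, two prognostic, R² 0.50 | 0.284 | 0.281 | -1% |

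Type I error under the rule was 0.050-0.051 with no prognostic factors and 0.040-0.047 with some.

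**5. How the covariate enters.** The planned two-time-point model was fitted to four simulated complete data sets, with and without a covariate as a main effect only. The group x time estimate was identical each time (for example -0.4764 in both fits). Adding covariate x time changed it (to -0.5433 in that example). So the form that the plan leaves open decides whether the sensitivity analysis can move the estimate at all.

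**6. A prespecified set.** With equal pre and post variances and pre-post correlation rho, change has SD sqrt[2(1 - rho)] and the baseline-adjusted post value has SD sqrt(1 - rho²). Their ratio is sqrt[(1 + rho)/2] = 0.866, 0.922, 0.949 at rho = 0.5, 0.7, 0.8, before the cost of the extra terms. Simulated mean SEs at n = 50, with ANCOVA on baseline plus two binary strata and about 25 non-prognostic candidates for the rule:

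| Assumed rho | Unadjusted change | Imbalance rule | ANCOVA, prespecified | ANCOVA vs unadjusted |
|---|---|---|---|---|
| 0.5 | 0.281 | 0.302 | 0.251 | 0.251/0.281, 11% smaller |
| 0.7 | 0.218 | 0.234 | 0.208 | 0.208/0.218, 5% smaller |
| 0.8 | 0.178 | 0.191 | 0.175 | 0.175/0.178, 2% smaller |

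The set should stay small. In a scenario with 20 weak predictors (joint R² 0.30), entering all 20 raised the SD from 0.284 to 0.314.

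**The case against.** The strongest reply is that little depends on this. The primary model has fixed terms, and the rule touches one of several supporting analyses; completer analyses, multiple imputation and models with expectancy and attention are also planned. The pilot says that it is not designed to detect significant differences, and the next trial's primary power analysis will rest on the minimal clinically important difference. All of that stands and limits the weight of the point.

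A second reply concerns precision. A reader might infer that adjusting for chance-imbalanced factors is always less precise than not adjusting. The documents do not support that, since they give no covariate-outcome correlations. The losses above assume independent candidates, and several of the listed scales (depression, anxiety, insomnia, sleep quality) plausibly correlate. With 25 candidates, three of them prognostic, an assumed common correlation of 0.3 removed the loss (mean SE 0.311 unadjusted, 0.312 with the rule), and at 0.5 the rule gained (0.329 to 0.316). The chance of at least one flag fell from 71% to 61% and 49%. This reply also stands.

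Neither reply defends imbalance as the reason for choosing a covariate.

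**Conclusion.** The concern holds as a criticism of the selection rule. It selects on chance rather than prognostic value, cannot be fixed in advance as written, tends to leave out the stratification factors and does not say how a covariate enters. The last-named tendency presumes that the stratified lists achieve balance; section 5.0 mentions no blocking.

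The consequence is confined to a sensitivity analysis. Three stronger readings are not supported:

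- **Invalid primary result.** The primary model selects nothing, and the rule did not inflate type I error.
- **A definite loss of precision.** The simulated change ran from about 10% worse to 1% better with independent candidates, and further in favour of the rule when candidates correlate. If covariates enter only as main effects, the group x time estimate does not change with complete data.
- **A large gain in power from the fix.** Such gains arise when the covariates are built to be strong predictors, and no figure in the documents supports that for the proposed set. The supported gain over unadjusted change is an SE about 2-11% smaller, for assumed pre-post correlations of 0.8 to 0.5.

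These sizes rest on p<0.05 as the meaning of differing, 10-30 candidates, 50 completers and the assumed correlations. The case for change rests on having a fixed and interpretable check more than on precision.

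**What to change.** In section 11.0, drop baseline differences as the basis for choosing covariates and for qualifying the interpretation, and describe baseline by arm without tests. Prespecify one adjusted analysis, the same for A1c and HOMA, with the pre-treatment value of the outcome, the A1c stratum and somatic symptoms (yes/no).

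State the model form, because the pre-treatment value is already a response in the planned mixed model and cannot simply be added as a covariate. Either of two forms would do:

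- ANCOVA on the post-treatment value, with arm and the three covariates; or
- a mixed model with the arms constrained to a common baseline mean and the strata interacting with time.

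For A1c, the stratum is a cut of the baseline value and will add little beyond it. It is kept because it was used in the randomisation.

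The cost is SAP wording only, since every variable is already collected. The change should be made before data are examined by arm.

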Weight, height, blood pressure, heart rate, respiration rate, and temperature will be measured by CRC nurses (pre, post). Validated questions/scales will assess demographics, medical/psychiatric history, current medications, alcohol use (AUDIT),⁷³ tobacco use (BRFSS Tobacco Use Questionnaire),^{119,120} physical activity (International Physical Activity Questionnaire),¹²¹ OHA adherence (Morisky Medication Adherence Scale-8),¹²²⁻¹²⁴ depressive symptoms (PHQ-9),^{74,75} anxiety (GAD-7),¹²⁵ hostility/anger (Buss-Perry Aggression Questionnaire),⁷⁶ trait positive affect (Positive Affect subscale of the PANAS),^{77,78} life satisfaction (Satisfaction with Life Scale),⁷⁹ insomnia symptoms (Insomnia Severity Index),⁸⁰ sleep quality (PSQI),¹²⁶ eating behaviors (Dutch Eating Behavior Questionnaire),⁸¹ quality of life (SF-20)⁸² (all pre, post), and expectancy of benefit⁸³ (pre). Attention will be determined from the intervention database for eIMPACT-DM patients and from EMR chart review for AC patients (post). Depression care variables (e.g., antidepressant dose/duration and psychotherapy session number/type) will be determined from the treatment delivery database for eIMPACT-DM patients and from EMR chart review for Active Control patients (post). Patients will complete a brief interview to assess depression care received outside of the trial (post). We will assess depression treatment acceptability (post). Diabetes prevention care received outside the trial will be assessed by EMR chart review (post) and a brief interview (post). We will also assess for the occurrence of any potential adverse events using a brief questionnaire and will administered the Techniques for Overcoming Depression Questionnaire⁸⁴ (post).

Type	Name	Time Frame	Brief Description
Hemoglobin A1c	Primary	Baseline, 6 months	The primary outcome is 6-month change in hemoglobin A1c, which will be measured at pre- and post-treatment by an immunoturbidimetric method on a Randox Daytona Clinical Analyzer in the Translation Core Analyte Lab of the Indiana CTSI. A1c is the gold standard glycemic outcome, ¹⁶ a strong predictor of future diabetes development, ^{17,18} and a potent indicator of improvement in clinical diabetes endpoints. ^{8,17,19,20}

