6.0 Study Design

We propose a pilot RCT of 64 primary care patients with a depressive disorder and prediabetes. Patients will be randomized to 6 months of eIMPACT-DM (our modernized collaborative stepped care intervention for depression) or the active control (depression education, symptom monitoring, and primary care for depression). The primary outcome is hemoglobin A1c – the gold standard glycemic outcome,⁶⁸ a strong predictor of diabetes development,^{69,70} and a potent indicator of improvement in diabetes endpoints.^{5,69,71,72} The secondary outcome is HOMA score, an established index of insulin resistance that correlates highly with the more invasive euglycemic clamp ($r=0.85-0.88$) and is appropriate for assessing change.⁸⁵⁻⁸⁸ We will also explore whether the presence of somatic depressive symptoms moderates the effect of eIMPACT-DM on diabetes risk markers (A1c and HOMA score).

In line with current conceptual frameworks,²⁷ we predict that eIMPACT-DM will improve A1c and insulin resistance by decreasing depressive symptoms and downstream factors (see figure). These downstream factors (grey boxes) are the leading candidate mechanisms by which depression treatment could reduce diabetes risk. First, substantial literatures indicate that depression is associated with each downstream factor (see A3). Second, intervention studies indicate that depression treatment (CBT or antidepressants) is related to improvements in autonomic dysfunction,⁸⁹⁻⁹² smoking,^{93,94} inflammatory markers,⁹⁵⁻⁹⁸ and insulin resistance.⁵¹⁻⁵³ Third, our post hoc analysis suggests that computerized CBT is associated with improvements in inflammatory markers and fasting glucose (see C2). While we expect that intervention-related reductions in depressive symptoms (paths a and b) will result in decreases in downstream factors (paths c, d, and e), some antidepressants could reduce A1c and insulin resistance via their direct effects on inflammation⁹⁹ and weight loss.^{100,101} We are not testing mechanisms in the proposed RCT (mechanistic trials are not allowed under PA-18-405); however, we plan to do so in the future definitive trial. Blue boxes indicate factors to be assessed in the proposed trial.

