7.0 Study Procedures

Trial Overview

Patients will attend the pre-treatment visit at the Clinical Research Center (CRC). They will fast and avoid tobacco and exercise for ≥ 8 hours. A finger-stick blood sample will be obtained to ensure patients have an A1c of $<6.5\%$. Those with an A1c outside of this range will not continue. Women able to become pregnant will also complete a urine pregnancy test, and those with a positive pregnancy test will not continue in the trial. Patients will complete questionnaires, an interview, anthropometric measurements, vital signs assessments (blood pressure, heart rate, respiration rate, and temperature), and standard venipuncture (to test A1c, HOMA scores, and insulin levels). Finally, randomization will occur. Six months after randomization, patients will return to the CRC for the post-treatment visit following the same procedures as the pre-treatment visit.

Trial Setting

The setting is the 8 primary care clinics of our clinical partner, Eskenazi Health, which is affiliated with Indiana University and is the second largest safety net healthcare system in the U.S. Eskenazi provides special opportunities to study diseases, like T2D,¹ that disproportionately affect lower SES ($\sim 90\%$ are underinsured/ uninsured) and minority ($\sim 50\%$ are racial/ethnic minorities) populations.

Participants

Please see sections 4.0 and 5.0 above.

Treatment Groups

1:1 randomization¹⁰² will be stratified by A1c ($\leq 6.09\%$, $6.10\text{-}6.49\%$) and somatic symptoms (yes, no).

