Treatment Process. At the end of the pre-treatment visit, our DCS will speak to the patient for 20 minutes via IU Zoom Health to orient them to depression materials and schedule the intake interview. Future DCS contacts will be over the phone or via IU Health Zoom, consistent with patient preference. Our DCS will contact the patient for the intake interview. At meetings every 2 weeks, the DCS will present cases to our team, who will formulate a Step 1 plan with PCP input. The DCS will work with the PCP to implement this plan. Step 1 will be 2 months of psychotherapy or an antidepressant. GDA and PST-PC are our first- and second-line psychotherapies; bupropion and fluoxetine are our first- and second-line antidepressants (others are third-line). For patients on an antidepressant at entry, the dosage may be increased, psychotherapy may be added, or a different antidepressant may be prescribed. For patients who want psychotherapy but have major barriers to GDA, PST-PC will be offered at Step 1. Our DCS will follow patients for 6 months, while monitoring response and staffing cases with the team at least every 2 months. At the start, the DCS will have sessions at least every 2 weeks. For patients who achieve remission ($\geq 50\%$ PHQ-9 reduction and < 3 symptoms⁵⁰), the DCS will develop a relapse prevention plan and follow-up monthly. Step 2 – augmenting Step 1 with psychotherapy or an antidepressant or switching to another psychotherapy or antidepressant – will be delivered to patients not in remission. If remission is not achieved after Step 2, Step 3 will be initiated, which will involve additional psychotherapy and/or antidepressants.

PHQ-9 Score	Action (within 24 hours)
<10 (minimal)	Results will be reported in a note added to the EMR.
10-19 (minor/moderate)	RA will encourage patient to seek treatment at their primary care clinic and will notify the patient's PCP and the embedded behavioral health clinician.
20-27 (severe)	RA will strongly encourage patient to seek treatment at their primary care clinic and will notify the patient's PCP, the embedded behavioral health clinician, and the affiliated psychiatrist.

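### Adding attention as a plain covariate cannot test attention as a rival explanation: it leaves the group x time estimate unchanged with complete data and almost unchanged with 20% missing

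*Combined protocol and SAP*

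**What the plan says.** - **The analysis.** Section 11.0 (Primary Aim Analytic Plan): "We will also add expectancy and attention as covariates in sensitivity analyses". Section 7.0 (Active Control) repeats the intention when it justifies the comparator, and concedes that the comparator cannot match attention patient by patient. Neither place mentions a covariate x time term.
- **The model.** Section 11.0 specifies a linear mixed model with an unstructured covariance and fixed effects for group, time and their interaction. The interaction carries the treatment effect.
- **Attention.** Section 3.0 (Other Factors): "Attention will be determined from the intervention database for eIMPACT-DM patients and from EMR chart review for AC patients (post"). No unit is given. The same section plans related data: "Patients will complete a brief interview to assess depression care received outside of the trial (post"), plus depression-care variables by arm. These are not named as a common measure of attention.
- **Timing.** Section 7.0 (Trial Overview) lists the pre-treatment assessments and then states "Finally, randomization will occur". All attention therefore comes after allocation.
- **Contact and response.** Section 7.0 (Treatment Process): "At the start, the DCS will have sessions at least every 2 weeks". For patients who remit, "the DCS will develop a relapse prevention plan and follow-up monthly". Patients not in remission go to the next treatment step.
- **Expectancy.** Section 3.0 lists "expectancy of benefit⁸³ (pre"), so it is a pre-treatment measure.
- **Mechanism.** Section 6.0: "We are not testing mechanisms in the proposed RCT".

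**The concern.** More staff contact in the intervention arm is an obvious non-specific explanation for any benefit, and section 7.0 places this adjustment beside the argument for the active control. A reader will expect the adjusted result to show whether the effect survives once contact is allowed for. Two features prevent that.

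First, the covariate has one value per patient, while the effect is a within-patient change. A constant cannot explain a change unless it is allowed to act differently at the two visits.

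Second, attention is a consequence of the assigned arm and, in the intervention arm, partly of how the patient responds. It is also recorded from different sources in the two arms, so any difference in recording is mixed up with group. Even a model in which attention can move the estimate would need an assumption that the plan does not state.

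If the literal analysis were reported as support for the main result, that support would be built in and not earned. The pilot is meant to help make the case for a definitive trial.

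**Working it through.** **The plan's own figure.** No figure is stated for the attention analysis. The stated power fixes the scale: a two-sided two-sample t-test with 25 per arm (48 df) gives 54.7%, 67.9%, 79.2% and 87.7% at d = 0.60, 0.70, 0.80 and 0.90. The plan states 55%, 68%, 79% and 88%, so these reproduce. The equation of 0.3% A1c with d = 0.50 implies an SD of 0.3/0.50 = 0.6%.

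**Why the term cancels.** Let G be group and A attention.

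- Pre: Y0 = b0 + b1·G + c·A + e0
- Post: Y1 = b0 + b1·G + b2 + b3·G + c·A + e1
- Change: D = Y1 − Y0 = b2 + b3·G + (e1 − e0)

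A is absent from D. With an unstructured covariance the likelihood splits into D, and Y0 given D. The second part has its own free intercept, group term, A term and slope on D, so it adds nothing about b3. With complete data b3 is the difference in mean change, with or without A. The same held when checked under a random-intercept covariance. No assumed input is needed. With dropout, patients who have only a baseline value let A leak in slightly.

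**Size by simulation.** Assumptions, none given in the documents: pre/post correlation 0.5, change SD 1, true effect −0.50, arms g = 2 SD apart in contact, 300 trials per setting. The share of the effect that runs through contact was set to 0%, 50% or 100%.

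| Quantity | 0% | 50% | 100% |
|---|---|---|---|
| Complete data, 25/arm: largest change in group x time from adding A | about 2e-15 | about 2e-15 | about 2e-15 |
| Complete data: SE ratio | 1.000 | 1.000 | 1.000 |
| 32/arm, 7/arm missing at random: mean absolute shift (SD) | 0.005 | 0.006 | 0.008 |
| Same: 95th percentile of shift (SD) | 0.014 | 0.021 | 0.028 |
| Attention x time instead: expected group x time | −0.50 | −0.25 | 0 |

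In repeat runs of the missing-data setting, no single trial shifted by more than about 0.07 SD (0.07 × 0.6 = 0.04 A1c points, against the 0.3 threshold). In a separate run in A1c units (SD 0.6%, assumed correlation 0.6), the 7 lowest-contact patients per arm dropped out. The mean shift was 0.004 to 0.008 points and the maximum 0.028.

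**What does move.** The adjusted between-arm difference moves by c times the gap in A. The shift is the same at both visits (almost the same with dropout). Its signed mean was about 0, 0.10 to 0.13 and 0.22 to 0.28 SD in the three cases. The model therefore adjusts baseline A1c for contact that had not yet occurred.

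**Precision with attention x time.** With equal arms the SE is multiplied by sqrt(1 + g²/4). The unadjusted 95% half-width is t(48) × sqrt(2/25) = 0.57 SD of change. The adjusted half-width is t(47) × sqrt(2/25) × sqrt(1 + g²/4).

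| Assumed g | SE multiplier | Half-width (SD) |
|---|---|---|
| 1 | 1.12 | 0.64 |
| 2 | 1.41 | 0.80 |
| 3 | 1.80 | 1.03 |

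**Bias with attention x time, illustration only.** Suppose contact correlates rho = 0.5 with non-response in the intervention arm only, non-response correlates r with A1c change, g = 2, and contact itself has no effect. The group estimate is then displaced by g × rho × r/2 = 0.05, 0.15 or 0.30 for r = 0.1, 0.3 or 0.6, which gives −0.55, −0.65 or −0.80 in place of −0.50. These values show the direction and mechanism and do not size a defect in this trial.

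**The case against.** The strongest reply has four parts.

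- **The wording does not exclude a time interaction.** True, but it does not include one either. Where section 11.0 wants a time interaction, for somatic symptoms and for sex, it writes the term out. The cancellation also applies to the baseline covariates in the same paragraph. That makes the missing term a general gap and widens the fix.
- **The literal model is not wholly insensitive.** This stands. Section 11.0 frames clinical importance as a post-treatment difference of at least 0.3%, and the adjusted version of that difference does respond on average. A reader might infer that every output would look reassuring, and that goes too far. As a check it is still poor: it shifts baseline equally, it is noisy, and its mean shift shrank to about 0.03 SD when low-contact patients were the ones who dropped out.
- **Each source is where that arm's contact is recorded.** Partly true. The symptom-monitoring table in section 7.0 sends some control-arm results to the EMR, and the treatment database holds the specialist's notes and EMR messages. A common unit and common sources are still missing.
- **It is only a sensitivity analysis in a pilot.** True. No decision rule uses it, and the plan says openly that attention cannot be matched exactly.

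A reader might also count scheduled contacts and infer that the arms cannot overlap in attention. The documents do not support this. Intervention sessions are set as a minimum frequency, problem-solving treatment adds eight weekly sessions for those who receive it, and control-arm attention from the EMR can include clinic care.

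**Conclusion.** The concern holds for this one sensitivity analysis. As written, the group x time estimate after adjustment for attention cannot show whether attention explains the result. The cancellation is exact with complete data and rests on algebra alone. At about 20% missing it is near-exact, with mean shifts under 0.01 SD in the scenarios run. Those figures, the interval widths and the bias illustration rest on the stated assumptions about the gap in contact and the correlations.

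Entering attention x time makes the estimate responsive. It then has a meaning only if no unmeasured factor drives both contact and outcome change. Response-driven stepping in the intervention arm makes that doubtful, and the plan does not state the assumption.

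A reader might infer that the main result is compromised, or that the sponsor intends to present this analysis as proof of robustness. Neither follows. The primary intent-to-treat analysis, the stated power and the d of 0.50 criterion are untouched, and the documents do not say how the adjusted result will be read. Nor is expectancy a post-randomisation covariate on the documents' ordering: it is listed at the pre-treatment visit, with questionnaires described before randomisation. Only its model term is at issue. The change should be made, but it is not critical to the trial.

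**What to change.** 1. Define attention in one unit, for example number or minutes of contact. Measure it in both arms from the same sources, study contact records plus EMR review, and report it descriptively by arm.
2. Do not present the estimate adjusted for attention as a main effect as a robustness check.
3. If an adjusted model is kept, enter attention x time and label it exploratory. State the assumption of no unmeasured common cause of contact and outcome change, and expect a wider interval. In line with section 6.0, do not read it as a test of mechanism. Say how patients without an attention value are handled, because dropping them would change the analysed sample.
4. Enter expectancy, and any baseline covariate used in the section 11.0 sensitivity models, with a time interaction. State when expectancy is taken relative to allocation, and note that a score taken before allocation does not capture expectancy that arises later.

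The cost is SAP wording, minor additional chart abstraction (section 3.0 and the treatment database in section 7.0 already cover much of the data), and the loss or relabelling of one sensitivity analysis.
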